5.9 EVALUATIONS AT THE END OF STUDY

The following assessments will be performed at Day 60 ± 3 or at the date of early study termination:

	ASSESSMENT/PROCEDURES
Clinical evaluation	
 COVID-19-related signs and symptoms checklist (Appendix 10 – COVID-19 signs/symptoms checklist). Clinical status (11-point WHO Clinical Progression Scale). Vital signs will include body temperature (°C), SBP (mmHg), DBP (mmHg), pulse rate (bpm) and respiratory rate (breaths/min). Targeted physical examination. A targeted physical examination will include heart, lungs, abdomen, extremities plus CNS assessment, based on the investigator's decision as per clinical evolution. Body weight will be measured in kilograms (kg). Lung function tests include PaO₂, FiO₂ and SpO₂. PaO₂/FiO₂ ratio will also be measured; either Ellis or Rice formulae can be used to estimate PaO₂/FiO₂ ratio (Appendix 5 – Imputation of PaO₂/FiO₂ ratio). 
 Concomitant therapies. Subsequent medications for SARS-CoV-2 infection. Subsequent medications for the underlying disease.
Laboratory tests*	
Haematology: haematocrit, RBC, differential WBC counts (including neutrophil and lymphocyte counts), platelet count and haemoglobin (See Appendix 8 – Clinical Laboratory Analyses).
 
Biochemistry: Liver function test [ALT, AP, AST¹, albumin, total bilirubin (direct bilirubin if total is

ASSESSMENT/PROCEDURES	
	abnormally elevated)], LDH, glucose [fasting], sodium, potassium, calcium, BUN/urea, GGT, creatinine, calculated creatine clearance [CKD-EPI], CPK, amylase, lipase, pro-calcitonin, ferritin, and CRP (See Appendix 8 – Clinical Laboratory Analyses).
	Coagulation: D-Dimer (See Appendix 8 – Clinical Laboratory Analyses).
	Urine analysis (semi-quantitative elemental tests for specific gravity, blood, pH, proteins, bilirubin, glucose, ketones, nitrites, and qualitative analysis of the sediment).
Inflammatory and immunological biomarkers in blood (central laboratory)	Luminex® Multiplex cytokine assessment.
Anti-SARS-CoV-2 (central laboratory)	IgG/M anti-protein S and N.
	T-cell response (IFN- γ) to SARS-CoV-2 S-protein (Quantiferon®).
Detection of SARS-CoV-2	qRT-PCR in oro/naso-pharyngeal exudates (central laboratory).
	Rapid Antigen Test (at site, provided by the Sponsor).
ECG**	Only if clinically indicated. Cardiac rhythm will be identified in ECG intervals of at least 30 seconds of duration, PR interval, QT interval (raw), heart rate and QRS complex, with specialist assessment/judgment of further evaluation if appropriate.
Chest X-ray	Qualitative evaluation and Brixia score (Appendix 9 – Brixia Score). (Submission to central review)
Survival status	
Hospitalization status	
Adverse events	As per NCI-CTCAE v.5***

* Central laboratory for all the test

** Triplicate.

*** The “AE form” will be used to report signs and symptoms and medical history in case of any significant change (improvement or worsening) during the study, as well as for events that occur after the first drug infusion or any event related to a study procedure within the study period (according to ICH guidelines).

[figure not shown]
¹See [Section 7.2.1 Adverse Events of Special Interest \(AESIs\)](#).

6. TREATMENTS

6.1 DESCRIPTION OF TREATMENTS

6.1.1 Drug Formulation and Supply

Plitidepsin 2 mg powder for concentrate for solution for infusion is presented as a sterile, preservative free, white to off-white lyophilised powder/cake in a 10 mL, single-dose, Ph. Eur. type I clear-glass vial.

Before use, the powder/cake is reconstituted with 4 mL of solvent for plitidepsin to give a solution containing plitidepsin 0.5 mg/mL. The reconstituted solution is diluted further in either sodium chloride 9 mg/mL (0.9%) solution for infusion (normal saline solution, NSS) or glucose 50 mg/mL (5%) solution for infusion (D5W) for IV infusion.

6.1.2 Storage conditions

Plitidepsin powder, 2 mg, must be stored at 5°C ± 3°C (2°C to 8°C). Keep the vials in the outer carton to protect from light.

Solvent for plitidepsin must be stored at 5°C ± 3°C (2°C to 8°C).

6.1.3 Administration of Study Medications

The IMP may be administered only by the Investigator or by a member of staff specifically authorised by the Investigator, as appropriate.

6.1.4 Treatment Schedule and Dose

Plitidepsin will be administered as a 60-min (±5 min) IV infusion, every 24 h (±30 min)* for 3 consecutive days, at a dose of 2.5 mg.

For prevention of infusion-related (i.e., plitidepsin-related) reactions (IRRs), allergic reactions and emesis reactions, administration of premedications is mandatory in the experimental arms.

*Treatment windows do not apply for the first 30 patients enrolled in this study (experimental arm) who will be included in the pharmacokinetics evaluations.

6.1.5 Prophylactic Medication

For prevention of plitidepsin related infusion reactions, the following premedications MUST be given to each patient and should be completed no more than ~2 hours to 20 minutes before initiating each plitidepsin infusion:

- Dexamethasone phosphate* 8 mg IV (equivalent to 6.6 mg of dexamethasone base);
- Dexchlorpheniramine maleate* 5 mg IV (or diphenhydramine hydrochloride 25 mg IV);
- Famotidine* 20 mg IV (or equivalent such as ranitidine 50 mg IV). Oral famotidine is acceptable, but in this case the dose should be 40 mg and it must be administered 2 hours (\pm 15 min) before plitidepsin;
- Palonosetron* 0.25 mg IV (tropisetron 5 mg IV could be considered if palonosetron is not available. It should be administered orally (PO)/IV on Days 4 and 5 if tropisetron 5 mg was administered on Days 1, 2 and 3).

*Provided by the Sponsor, who is also in charge of the labeling (except when the site uses its own medication for the trial).

6.2 DOSE REDUCTION

Not applicable

6.3 CONCOMITANT MEDICATION

6.3.1 Allowed Medications/Therapies

Any medications, with the exceptions noted in [Section 6.3.2](#) below, which are considered necessary for the patient's welfare, and which will not interfere with the study medication, may be given at the discretion of the Investigator. Medications which MUST be administered as part of the study treatment schedule are listed in [Section 6.1.5](#).

Administration of **all concomitant drugs** received by the patient during the "on-treatment" period of the trial must be reported in the appropriate section of the eCRF along with dosage information, dates of administration and reasons for use. Additionally, any unplanned diagnostic, therapeutic or surgical procedure performed during the study period must be recorded in the eCRF.

6.3.2 Prohibited Medications/Therapies

- Other investigational agents.
- Concomitant use of plitidepsin and antiviral treatments for COVID-19.

- Strong CYP3A4 inhibitors and inducers throughout plitidepsin treatment period and until 24-h washout period ([Appendix 3 - Inhibitors and Inducers of CYP3A4](#)), unless medical judgement that they are for the patient's best interest.

Investigator may decide to stop the study treatment at any time after the first dose of plitidepsin and initiate other antiviral treatments for COVID-19.

6.3.3 Drug-drug Interactions with Plitidepsin

There have been no clinical studies on drug interactions. Effect of other medicinal products on plitidepsin include:

Interactions with CYP3A4 inhibitors and inducers: *In vitro* studies indicate that CYP3A4 is the major enzyme involved in plitidepsin metabolism, followed by CYP2A6 and CYP2E1. However, a pharmacokinetic population analysis of plitidepsin including 283 patients indicated that concomitant administration of CYP3A4 inhibitors and inducers does not affect exposure to plitidepsin. Nevertheless, it cannot be ruled out that concomitant treatments that inhibit or induce CYP3A4 may modify the efficacy and/or increase the probability of side effects associated with plitidepsin, so they should be avoided.

- Co-administration of plitidepsin with strong CYP3A4 inhibitors and inducers should be avoided, as they may affect the plasma concentration of plitidepsin, unless medical judgement that they are for patient's best interest.
- Co-administration with moderate CYP3A4 inhibitors and inducers should be used with caution, as an effect on plitidepsin exposure cannot be excluded.

Interactions with CYP3A4 inhibitors: Plitidepsin should not be administered with potent inhibitors CYP3A4 (e.g. grapefruit juice, clarithromycin, itraconazole, nefazodone, telithromycin, voriconazole). Potent inhibitors CYP3A4 should be discontinued before starting treatment and during treatment with plitidepsin. They may be re-administered 24 hours after the last dose of plitidepsin.

Moderate inhibitors CYP3A4 (e.g., aprepitant, diltiazem, erythromycin, fluconazole, verapamil) should be used with caution, as increased exposure to plitidepsin cannot be excluded

Interactions with CYP3A4 inducers: To avoid a decrease in the effectiveness of plitidepsin, plitidepsin should not be administered with potent inducers of CYP3A4 enzyme, such as anticonvulsants (phenytoin, phenobarbital or carbamazepine), rifampicin, rifabutin and St.John's wort, unless there are no therapeutic alternatives. The appropriate initial dose for patients taking potent inducers has not been defined.

They may be administered again 24 hours after the last dose of plitidepsin. CYP3A4 moderate inducers (e.g., bosetan, modafinil, naftilin) should be used with caution, as a reduction of exposure to plitidepsin cannot be excluded. A list of CYP3A4 inducers and inhibitors is included in [Appendix 3 - Inhibitors and Inducers of CYP3A4](#).

Effect of plitidepsin on other drugs: *In vitro* studies did not show a potential for plitidepsin to inhibit or induce metabolism of other drugs. However, the results for ruling out the potential inducing effect of plitidepsin on the CYP2B6 enzyme were inconclusive. The potential effect of

plitidepsin on CYP2B6 has not been studied *in vivo*. Therefore, decreases in plasma concentrations of drugs that are substrates of this enzyme cannot be ruled out when co-administered with plitidepsin.

The use of any herbal/natural products or other "folk remedies" should be discouraged, but use of those products, as well as the use of vitamins, nutritional supplements, and all other concomitant medications must be recorded in the eCRF.

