DRUG-DRUG INTERACTIONS WITH PLITIDEPSIN	
Interactions with CYP3A4 inhibitors and inducers: In vitro studies indicate that CYP3A4 is the major enzyme involved in plitidepsin metabolism, followed by CYP2A6 and CYP2E1. However, a pharmacokinetic population analysis of plitidepsin including 283 patients indicated that concomitant administration of CYP3A4 inhibitors and inducers does not affect exposure to plitidepsin. Nevertheless, it cannot be ruled out that concomitant treatments that strongly inhibit or induce CYP3A4 may modify the efficacy and/or increase the probability of side effects associated with plitidepsin, so they should be avoided.
 
 • Co-administration with CYP3A4 strong inhibitors and inducers should be avoided, as they may affect the plasma concentration of plitidepsin, unless medical judgement that they are for the patient's best interest. • Co-administration with CYP3A4 moderate inhibitors and inducers should be used with caution, as an effect on plitidepsin exposure cannot be excluded. 
A list of CYP3A4 inducers and inhibitors is included in Appendix 3 - Inhibitors and Inducers of CYP3A4.

DOSE REDUCTION	No dose modifications are foreseen at the experimental arm.
SAFETY EVALUATION CRITERIA	
Safety parameters/covariates include:
 
 • Demographic Data including gender and age; • Medical history and prior medications and procedures; • ISARIC 4C Mortality & 4C Deterioration scores (Appendix 4); • AEs will be monitored throughout the study, which will start immediately after the patient Informed Consent Form (ICF) is signed;

	
 • Pregnancy; • Concomitant medications and procedures; • Physical examination including height and weight. Body Mass Index will be calculated; • Vital signs include body temperature (°C), systolic blood pressure (SBP) (mmHg), diastolic blood pressure (DBP) (mmHg), pulse rate (bpm) and respiratory rate (breaths/min); • Laboratory tests include haematology, coagulation and biochemistry; • Urinalysis; • Electrocardiograms (ECGs) include overall assessment, heart rate (HR), PR interval (PR), QRS duration (QRS), uncorrected QT interval (QT), and corrected QT interval by Fredericia (QTcF), and will be performed at the study site.

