11.4 Protocol Deviations

A protocol deviation is defined as any departure from what is described in the protocol of a clinical trial. The study specific Protocol Deviation Guidance Document defines all important protocol deviations.

The study team will conduct on-going reviews of the deviation data and document must be finalized prior to database lock.

Summaries of protocol deviations will be produced.

Deviations with no effects on the risk/benefit ratio of the clinical trial (such as minimal delays in assessments or visits) will be distinguished from those that might have an effect on this risk/benefit ratio.

Below examples of deviation's classification are listed.

████████████████████

Table 2 Important protocol deviations.

Category	Sub Category	Project Specific Protocol Deviation
Study Conduct/ Procedures	Inclusion/ Exclusion Criteria	Failure to complete or comply with inclusion/exclusion criteria
Study Conduct/ Procedures	Screening	Non-compliance with screening procedure protocol requirements to confirm eligibility of the patient
Study Conduct/ Procedures	Study Restrictions/ Withdrawal	Non-compliance with protocol restrictions (e.g. use of prohibited medication or prohibited treatment therapy)
Study Conduct/ Procedures	Dose Formulation/ Dose Administration	Administration Use of prohibited medication
Study Conduct/ Procedures	Dose Formulation/ Dose Administration	Incorrect study drug dose, frequency, timing or method of drug delivery (e.g. subject overdosed with study drug, incomplete study drug administered), incorrect volume of infusion
Study Conduct/ Procedures	Dose Formulation/ Dose Administration	Study drug dosing adjustments performed outside of Protocol

All-important protocol deviations leading to exclusion from any population occurring during the study will be reviewed and approved by Pharma Mar prior to database lock.

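### The protocol sets conflicting exception tests for giving plitidepsin with strong CYP3A4 inhibitors or inducers, so the same use can be permitted by one passage and not by another

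*Protocol*

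**What the plan says.** **Rule with a best-interest exception.** Protocol 6.3.2 lists as prohibited "Strong CYP3A4 inhibitors and inducers throughout plitidepsin treatment period and until 24-h washout period", then adds "unless medical judgement that they are for the patient's best interest". The synopsis carries the same exception in its rows on prohibited medications and on drug-drug interactions. So does the first bullet of 6.3.3: "Co-administration of plitidepsin with strong CYP3A4 inhibitors and inducers should be avoided, as they may affect the plasma concentration of plitidepsin, unless medical judgement", followed by the best-interest condition.

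**Later paragraphs of 6.3.3.**
- On inhibitors: "Plitidepsin should not be administered with potent inhibitors CYP3A4", with clarithromycin, itraconazole and voriconazole among the examples, and "Potent inhibitors CYP3A4 should be discontinued before starting treatment and during treatment with plitidepsin". No exception is stated.
- On inducers: plitidepsin should not be given with potent inducers (phenytoin, carbamazepine and rifampicin are among those named) unless no other treatment is available. The paragraph adds: "The appropriate initial dose for patients taking potent inducers has not been defined".

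**Dose.** Protocol 6.1.4 gives a single daily dose of 2.5 mg on 3 consecutive days. The synopsis states "No dose modifications are foreseen at the experimental arm", and 6.2 marks dose reduction as not applicable. No exclusion criterion in 4.2 names CYP3A4 inhibitors or inducers.

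**Deviations.** SAP 11.4, Table 2, lists among important protocol deviations "Non-compliance with protocol restrictions (e.g. use of prohibited medication or prohibited treatment therapy").

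**The concern.** A site needs one answer to whether a patient who needs a strong CYP3A4 inhibitor or inducer may receive plitidepsin. The protocol gives more than one, and the difference lies in the exception, which is where a borderline patient is decided. The conflict also sits inside 6.3.3, whose opening bullet grants an exception that its later paragraphs drop for inhibitors and replace for inducers.

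Two things are at stake. The first is patient handling: two sites could treat identical patients differently and each cite the protocol. Protocol 5.2.2 ends treatment for a major deviation that may affect the patient's risk/benefit ratio, and 5.3 does not allow deviations of that kind to be authorised. Whether a use counts as a deviation can therefore have consequences beyond bookkeeping. The second is deviation coding, since prohibited-medication use is a Table 2 category and whether a drug was prohibited depends on the passage read.

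**Working it through.** No arithmetic applies, so the check is a side-by-side reading. It treats strong (6.3.2, the synopsis and the 6.3.3 bullets) and potent (later 6.3.3) as the same class, because 6.3.3 sets each against moderate agents in the same way. Appendix 3, which lists the drugs, is not in the text available for review.

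**Step 1. Apply each rule to a patient whose physician judges the drug to be in the patient's best interest.**

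| Patient's drug | Synopsis, 6.3.2, first bullet of 6.3.3 | Later paragraphs of 6.3.3 | Result |
|---|---|---|---|
| Strong inhibitor (e.g. voriconazole) | Permitted | Not permitted; should be stopped | Conflict |
| Strong inducer, alternative exists (e.g. carbamazepine) | Permitted | Not permitted | Conflict |
| Strong inducer, no alternative | Permitted | Permitted | Agree on co-administration; dose called undefined |

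The first two rows are direct conflicts. They arise from the differing exceptions alone.

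**Step 2. Dose with inducers.** In the third row both sets of rules let the patient in. Section 6.3.3 then says the initial dose for that patient is undefined, while 6.1.4, 6.2 and the synopsis leave only the flat dose. This is a separate inconsistency: the protocol admits a patient and prescribes a dose that it also describes as not established for that patient.

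**Step 3. Strength of inhibitor or inducer.** The lead-in of 6.3.3 says that treatments which inhibit or induce CYP3A4 should be avoided, with no qualifier. The matching sentence in the synopsis limits this to those that do so strongly. Both places then allow moderate agents with caution, so the unqualified lead-in disagrees with the bullet beneath it. This is the smallest of the three mismatches.

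**Step 4. Timing.** Section 6.3.2 runs its restriction to a 24-h washout. Section 6.3.3 lets both inhibitors and inducers resume 24 hours after the last plitidepsin dose. These agree.

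**Step 5. Reach into the analysis.** The SAP was abridged after the closure decision of 23 February 2024. SAP 8.6.2.1 does not exclude patients from the FAS for deviations, 8.6.2.2 drops per-protocol outputs, and 11.10 drops subgroup outputs. Deviation summaries (11.4), concomitant-medication tables (11.5) and safety tables (11.7) remain.

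**The case against.** The best counter-argument is that the operative rule is consistent. Section 6.3.1 sends sites to 6.3.2 for prohibitions, and 6.3.2, the synopsis and the first bullet of 6.3.3 share one exception, so the later text of 6.3.3 is only explanatory and is worded as advice (should). This does not remove the conflict. Those paragraphs tell the site to withhold or stop a drug, nothing ranks them below 6.3.2, and the advisory wording does not supply the missing exception.

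Other objections stand, and they limit the point. A reader might infer any of the following, none of which the documents support:

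- **That the undefined inducer dose itself makes a patient both allowed and prohibited.** It does not. It states a limit of knowledge and is a separate inconsistency with the flat dose.
- **That the washout periods contradict each other.** They agree on 24 h after the last dose. Neither section states an interval before the first dose, but that is a shared gap. Screening may run up to 48 h before treatment, so same-day dosing after randomisation does not rule out stopping a drug.
- **That altered exposure is established.** The synopsis and 6.3.3 cite a population PK analysis of 283 patients indicating that CYP3A4 inhibitors and inducers do not affect plitidepsin exposure, then say an effect on efficacy or side effects cannot be ruled out.
- **That every plitidepsin patient is affected.** Only those on or needing these drugs are.
- **That deviation status is settled by Table 2.** SAP 11.4 says a separate guidance document defines all important deviations and introduces its own list as examples. That document is not available here, so the most that can be said is that the same use could be coded either way.

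**Conclusion.** The conflict is real and can be confirmed by reading the passages together. For a strong inhibitor judged necessary, and for a strong inducer judged necessary where an alternative exists, the protocol both permits and does not permit co-administration. The undefined-dose statement and the unqualified lead-in of 6.3.3 are further, lesser inconsistencies.

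The size cannot be given as a number, because the documents do not say how many patients were taking or needed these drugs. The possible harm is one the protocol declines to exclude, not one it documents. With recruitment over and per-protocol and subgroup outputs dropped, the planned efficacy summaries do not depend on this point. What remains is the coding of deviations, the description of co-administration, and the risk of carrying the same text into another protocol. The conclusion assumes that strong and potent mean the same class and that Appendix 3 and the deviation guidance document do not already resolve the matter. No position is taken on which rule or dose is right.

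**What to change.** 1. Reconcile the two synopsis rows, 6.3.2 and 6.3.3 into one consistent rule with one exception test for each drug class (strong inhibitors, strong inducers, moderate agents), and bring the lead-in of 6.3.3 into line with the synopsis. The content of the rule is for the sponsor to decide.
2. Reconcile the statement that the initial dose with potent inducers is undefined with 6.1.4, 6.2 and the synopsis.
3. Record the reconciled rule in the deviation guidance and code prohibited-medication deviations by it before the deviation summaries are finalised.
4. List patients who received a strong inhibitor or inducer with plitidepsin, using the concomitant-medication data that SAP 11.5 already codes.

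The cost is a short clarification note, a coding convention and one listing, with no new data collection. Site retraining would bring little now that recruitment has ended, and safety tables split by co-administration are hard to justify in a SAP that has dropped subgroup outputs. If the text is reused, it should be reconciled first.

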6.4 DRUG ACCOUNTABILITY

Proper drug accountability will be done by the appropriate trained study personnel. Each study site will keep records to allow a comparison of quantities of drug received and used at each site for monitoring purposes. The Investigator at each study site will be the person ultimately responsible for drug accountability at the site.

All unused drug supplied by the Sponsor will be properly destroyed at the study site. Documentation of this procedure must be provided to the clinical trial monitor. If the Sponsor agrees, unused drug supplies may be returned to the drug repository.

